3.4 Study Assessments

During the course of the study, participants will frequently undergo assessments of their insulin production, immunologic status, overall health and well-being and diabetes care (see schedule of assessments in Appendix A). Information about the subject's experience as a research participant will also be collected. The participants' insulin production will be measured by a series of mixed meal glucose tolerance tests (MMTT) conducted regularly during the study. The participants' diabetes control will be evaluated by measuring glycosylated hemoglobin (HbA1c) and clinical records including insulin types, doses, and timing and SMBG records. During the course of the study, samples will be drawn for storage in the National Institute for Diabetes and Digestive and Kidney Disease (NIDDK) Repository and at TrialNet Sites for future analysis.

3.5 Quality Assurance

During the study, duplicate collections of blood samples for assays will be obtained in a small sample of subjects for the purpose of quality surveillance of the performance of the central laboratories.

3.6 Post-treatment Follow-up

At the conclusion of the study or when subjects reach 24 months, subjects will be encouraged to participate in further follow-up via participation in the TrialNet Long Term Investigative Follow-Up (LIFT).

4 PATIENT MANAGEMENT

4.1 Overview

Eligible subjects will receive either: (1) ATG (2.5mg/kg) IV followed by GCSF SQ (for those ≥ 44.5 kg, the dose is 6mg; for those <44.5 kg, the doses is 100 mcg/kg q 2 weeks x 6 doses), (2) ATG (2.5mg/kg) IV plus placebo, or (3) double placebo. Subjects will undergo screening visits to determine eligibility. Within 8 weeks of screening but preferably less than 37 days, eligible subjects will be admitted to an inpatient hospital or research facility for visit 0 and will be randomized to one of three treatment groups (ATG/GCSF, ATG/Placebo, and Placebo/Placebo). Individuals will receive oral and IV premedication and the first dose of ATG/placebo will be administered over a minimum of 12 hours (maximum of 20 hours) (Figure 4). CBC will be drawn 8 hours after the completion of dose 1 and will inform timing for infusion number 2. If labs are above threshold and at least 12 hours have passed since the completion of the first dose, the second dose of ATG/placebo will be administered over a minimum of 8 hours (maximum of 16 hours). Each ATG/placebo dose will be followed by steroid/saline infusion. The first dose of GCSF/Placebo will be given 6 hours after the end of the second ATG/placebo dose. Subsequent GCSF/placebo will then be given as outpatient every 2 weeks for a total of 6 doses over 5 visits. Subsequent visits will occur every 3-6 months through 24 months.

[figure not shown]

Figure 4. Minimum and Maximum Time Course for ATG Infusion and Hospitalization.

The top half of the figure demonstrates the ideal scenario for ATG infusion: First dose of ATG (0.5mg/kg) completed over 12 hours, CBC drawn 8 hours post infusion, second dose (2mg/kg) completed over 8 hours, first GCSF dose given 6 hours after completion of ATG, and D/C 12 hours after completion of ATG. The bottom half of the figure demonstrates the maximum allowable time for ATG infusion and first GCSF dosing if laboratory abnormalities or patient care issues require interrupting, postponing, or reducing the rate of ATG infusion

4.2 Screening

After informed consent, subjects will undergo assessments to determine if they meet eligibility criteria. Documentation of the subjects understanding of the risks and benefits of the study will be collected through the Volunteer Understanding Assessment.

4.3 Randomization

Eligible study participants will be randomized by the TrialNet Coordinating Center at the baseline visit once eligibility has been confirmed. Subjects will be assigned a study randomization number corresponding to the treatment group assignment.

4.4 Intensive Diabetes Management

During the study period, all participants will receive “intensive” management of their diabetes. The goal of the treatment will be to keep the HbA1c levels within the currently recommended American Diabetes Association age-specific target range in the absence of significant or severe hypoglycemia or diabetic ketoacidosis. The primary responsibility for diabetes management will be the treating or referring diabetes care provider, but the research study team will provide close additional support through regular interaction. Subjects will not be permitted to use non-insulin pharmaceuticals for glycemic control.

Glucose levels should be checked frequently and records of the glucose levels communicated regularly to the study team. Records of communication with the participant will provide source documentation of this interaction.

The Clinic Monitoring Group (or designated TrialNet Committee) will be evaluating the HbA1c data and provide additional guidance to the clinical site as needed to bring diabetes control within goals. Any episode of severe hypoglycemia will be promptly reviewed by the Safety Monitoring Committee with recommendations for changes in diabetes management, if any, conveyed to the clinical site in conjunction with the Clinic Monitoring Group.

4.5 Drug Administration

4.5.1 ATG

ATG is indicated for the treatment of renal transplant acute rejection in conjunction with concomitant immunosuppression. Each 10 mL vial contains 25 mg ATG (rabbit) as well as 50 mg glycine, 50 mg mannitol, and 10 mg sodium chloride.

4.5.2 ATG / Placebo Administration

All participants will be admitted to the hospital for the duration of the infusions and will be discharged no sooner than 12 hours after ATG infusion has been completed. Body weight at baseline (Time 0 – admission for the ATG/placebo infusion) will be used in calculating the doses for all infusions. Allowance in dose administration will be within +/- 5% of calculated dose.

To minimize the risk for thrombophlebitis associated with ATG infusion, 1000 units of heparin and 20 mg of hydrocortisone will be added to the ATG infusion bag for each dose given via peripheral intravenous administration. Since there is only a slight risk for thrombophlebitis for placebo infusion, the heparin and hydrocortisone will not be included in the infusion bag.

The first dose (0.5mg/kg) will be infused over a minimum of 12 hours, and the second dose (2mg/kg) over a minimum of 8 hours. The second dose should be given no less than 12 and no more than 24 hours after the previous dose. A maximum of 60 hours from the start of the first IV infusion will be allowed to complete all IV study drug (see parameters below). If a subject has not completed the two IV study drug infusions at the 60th hour, the infusion will be discontinued and they will not receive additional study drug. Vital signs will be checked every 30 minutes for the first 2 hours of the study drug infusion and thereafter at 60-minute intervals or as indicated for clinical signs or symptoms. Blood for laboratory testing should be drawn at least 8 hours after completion of each infusion in order to obtain reliable and comparable results.

Information about subject's clinical signs and symptoms related to ATG infusion will be captured on infusion CRFs. Those that are Grade 2 or more will be considered AEs and reported as such.

4.6 Premedication:

To reduce the risk of adverse reactions to ATG infusion, methylprednisolone 0.25 mg/kg IV will be given no less than 30 minutes before each infusion of active drug and 0.25 mg/kg IV will be given 12 hours (\pm 15 min) after the start of each infusion of active drug.

Placebo group: A placebo (saline) infusion similar in appearance will be given no less than 30 minutes before and 12 hours (\pm 15 min) after the start of each infusion.

Both groups: Participants in both groups will be pre-medicated with an antihistamine and acetaminophen PO at least 30 minutes before each infusion and every 4–6 hours as needed during the infusion, as follows:

- Diphenhydramine 1.25 mg/kg/dose to a maximum of 50 mg.
- Acetaminophen 10–15 mg/kg/dose to a maximum of 650 mg.

4.6.1 Cytokine Release Syndrome:

With ATG infusion, the subject may experience Cytokine Release Syndrome (CRS). The signs and symptoms can span a wide clinical spectrum.

Mild Reactions: For mild (grade 1) reactions per the NCI-CTCAE for CRS, the study medication will be continued. The investigator shall take one or more of the following actions, depending on the type of the reaction:

1. Administer additional doses of antihistamine and acetaminophen.
2. Reduce the rate of infusion by 50% or more.
3. For chills and rigors, meperidine may be considered.

Moderate Reactions: For moderate (grade 2) reactions per the NCI-CTCAE for CRS, the study medication may be interrupted. The investigator shall take the following actions, depending on the type of the reaction:

1. Interrupt infusion if any of the following occurs:
 - a. Oral temperature of $> 40.0^{\circ}\text{C}$
 - b. Symptomatic bronchospasm or pulmonary edema
 - c. Allergy-related edema
 - d. Hypotension
2. When the temperature is $< 38.5^{\circ}\text{C}$ and signs and symptoms improve, restart ATG.
3. Closely monitor the subject with pulse oximetry and a blood pressure monitoring; provide ongoing nursing evaluation until at least 2 hours after the infusion is completed.
4. If necessary, glucocorticoids can be given every 6 hours at a dose of 0.5 mg/kg of methylprednisolone or equivalent.
5. If a subsequent dose of ATG further exacerbates the signs and symptoms of CRS despite following the above guidelines, the study treatment must be permanent discontinued.
6. Additional supportive or resuscitative measures (such as the use of epinephrine) may be needed if clinically indicated.

Severe Reactions: For severe (grade 3) reactions or greater per the NCI-CTCAE for CRS, the study medication will be permanently discontinued.

[figure not shown]

Figure 5. Rate Adjustments in Response to Cytokine Release Syndrome

4.6.2 Allergic Reactions

Hypersensitivity: In rare cases, patients may experience hypersensitivity, which refers to immediate allergic, IgE mediated reactions to ATG. Such patients primarily develop skin rash and respiratory distress early in the course of the infusion (usually within the first hour). For such reactions, the investigator shall take one or more of the following actions:

1. Discontinue the infusion.
2. Apply appropriate resuscitation measures, including administration of 0.3–0.5 mL aqueous epinephrine (1:1000 dilution) subcutaneously.
3. Use other resuscitative measures, as clinically indicated, including oxygen, intravenous fluids, antihistamines, corticosteroids, pressor amines, and airway management.

Mild to Severe Reactions: For mild to severe (grade 3 or less) reactions per the NCI-CTCAE for allergic reactions, the study medication may be restarted at the discretion of the investigator. For those with severe (grade 3) reactions, any subsequent doses should be accompanied by pre-medication with additional corticosteroids.

Life-threatening Reactions: For life-threatening (grade 4) reactions per the NCI-CTCAE for allergic reactions, the study medication will be permanently discontinued.

[figure not shown]

Figure 6. Rules for Temporary interruption or discontinuation of ATG due to Hypersensitivity Reaction

4.7 Modification or Discontinuation of ATG

4.7.1 Modification of second ATG dose to 1mg/kg

All ATG must be administered by the end of 60 hours. CBC with differential will be obtained 8 hours after the completion of infusion 1. If initial labs show acceptable values (WBC count >2,000 cells/mm³, neutrophil count >1,200 cells/mm³, and platelet count >75,000 cells/mm³), ATG will be continued at the full dose. If labs are outside of these parameters a second CBC can be obtained up to 24 hours after completion of the infusion.

The second ATG/placebo dose will be reduced from 2mg/kg to 1mg/kg if both the a 8 hour post infusion AND 24 hour post infusion platelet counts fall between 50,000 and 75,000 cells/mm³, or if the neutrophil count falls to a value >800 but <1,200 cells/mm³. Although the ATG package insert recommends reducing the dose by 50% if a patient has a total white blood cell (WBC) count of between 2000 and 3000 cells/mm³, it has been decided not to reduce the dose in this protocol for the following reasons:

- Because the primary focus of this study is initial T-cell depletion, premature or unnecessary reduction of the ATG dose may result in reduced efficacy.
- If the WBC count falls to a significantly lower level, i.e. <2000 cells/mm³, then ATG will be held

- Participants will be closely monitored for infectious disease risk and offered prophylaxis as warranted to minimize their risk
- GCSF is expected to minimize the time/severity of neutropenia

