4.7.2 Discontinuation of ATG

The ATG/placebo will be discontinued if any one of the following is observed:

- A total WBC count $<2,000$ cells/mm³ that persists up to 24 hours after the time of the planned infusion.
- A neutrophil count <800 cells/mm³ that persists up to 24 hours after the time of the planned infusion.
- A platelet count $<50,000$ cells/mm³ that persists up to 24 hours after the time of the planned infusion.
- The participant experiences exacerbation of Cytokine Release Syndrome (CRS) twice consecutively despite the use of glucocorticoids.
- If the investigator believes that the study treatment is no longer in the best interest of the participant

Participants who prematurely discontinue study treatment will remain in the study and undergo all efficacy and safety assessments.

[figure not shown]

Figure 7. Rules for Reducing or Holding Second Dose of ATG

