APPENDIX 1 - Schedule of Assessments

Week of Trial					2	4	6	8	10						
Month of Trial										3	6	9	12	18	24
Day of Trial		0	1	2											
Visit number	-1	0 ^A	0 ^B	0 ^C	1	2	3	4	5	6	7	8	9	10	11
ATG/Placebo: Infusion 1 and 2			X	X											
GCSF/Placebo q 2 wk ⁶				X	X	X	X	X	X						
History	X	X													
Physical exam ⁸	X	X			X	X	X	X	X	X	X	X	X	X	X
TB Test – IGRA	X														
CBC with differential ² (local)	X		X		X	X	X	X	X	X	X	X	X	X	X
CD4/CD8 Ratio ³		X				X		X		X	X	X	X		
Chemistries	X	X			X	X	X	X	X	X	X	X	X	X	X
Pregnancy test (if female of reproductive potential)	X	X			X	X	X	X	X	X	X	X	X	X	X
Urinalysis	X	X			X	X	X	X							
Flu Vaccination ⁷	X														
HIV, Hep B, Hep C serology	X														
IgG		X													
EBV and CMV serology and PCR ⁴	X												X		
Serum for autoantibodies	X														
Mechanistic Assessments ⁵		X	X	X	X	X	X	X	X	X	X	X	X	X	X
Adverse Events Assessments ⁶			X	X	X	X	X	X	X	X	X	X	X	X	X
Hemoglobin A1c	X									X	X	X	X	X	X
Mixed Meal Tolerance Test (2 hr)										X	X	X			
Mixed Meal Tolerance Test (4 hr)	X												X	X	X
Diabetes Assessment		X			X	X				X	X	X	X	X	X

² CBC obtained 8 hours after completion of infusion 1. CBC can be repeated up to 24 hours after completion of infusion 1 if initial CBC is abnormal. The repeat CBC will inform dosing for infusion 2.

³ CD4/CD8 ratio will continue to be monitored until the CD4 count is above 500. CD4/CD8 ratio can be collected at screening visit or baseline Visit 0^A and may also be done at local laboratory if necessary to obtain results.

⁴ Viral PCR/Serology: All subjects will have serology and PCR for EBV and CMV at screening and at 1 year. Subjects who are EBV serology negative at screening must be PCR negative within 30 days of receiving ATG/Placebo. Additional EBV PCR testing may be obtained locally if necessary to obtain results within study windows. Subsequent EBV PCR/Serology will only be performed for symptomatic subjects who were EBV seronegative at screening. Subsequent CMV PCR will be performed for symptomatic subjects regardless of initial CMV serology status.

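### The rules for reducing or stopping the second ATG/placebo dose leave two platelet courses unassigned, allow two readings for neutrophils and run on different clocks

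*Protocol*

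**What the plan says.** Six places in the protocol govern the second infusion.

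- **4.1 Overview.** Dose 2 goes ahead if laboratory values are above threshold and at least 12 h have passed since dose 1 was completed. The threshold is not defined there. Infusion 1 lasts 12 to 20 h and infusion 2 lasts 8 to 16 h.
- **4.5.2.** "The second dose should be given no less than 12 and no more than 24 hours after the previous dose". All IV study drug must be complete within 60 h of the start of infusion 1.
- **4.7.1.** A blood count is taken 8 h after infusion 1. If white cells and neutrophils are also acceptable, the rule is: "platelet count >75,000 cells/mm³), ATG will be continued at the full dose". Otherwise "a second CBC can be obtained up to 24 hours after completion of the infusion". Dose 2 is halved "if both the a 8 hour post infusion AND 24 hour post infusion platelet counts fall between 50,000 and 75,000" cells/mm³, or if neutrophils lie between 800 and 1,200. The neutrophil limb names no time point.
- **4.7.2.** ATG/placebo is discontinued for platelets below 50,000, neutrophils below 800 or white cells below 2,000, in each case "that persists up to 24 hours after the time of the planned infusion". It is also discontinued if the investigator judges it no longer in the participant's best interest.
- **Appendix 1, footnote 2.** After an abnormal first count: "The repeat CBC will inform dosing for infusion 2".
- **Figure 7.** By its caption it covers reducing or holding the second dose. It is not visible in this copy.

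**The concern.** A site must be able to take two blood counts and arrive at one action. Here the platelet reduction needs two in-band values and the discontinuation needs a persisting low value, so a participant whose platelets cross 50,000 between the two counts can fall between the rules. The neutrophil limb and footnote 2 can point to different doses for the same results. The times at which the rules are to be evaluated do not match the time by which the dose should be given.

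These are safety rules in a trial that enrols from age 12. Two sites could give the same participant different second doses while each follows the protocol. ATG exposure in two of the three arms would then depend partly on which section was read.

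**Working it through.** **1. Check the clock.** The 60 h cap can be rebuilt from the protocol's own maxima: longest infusion 1 (20 h) + longest gap (24 h) + longest infusion 2 (16 h) = 60 h. This matches 4.5.2, so the 24 h gap limit runs from completion of infusion 1. The 12 h minimum in 4.1 uses the same anchor.

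**2. Apply 4.7.1 and 4.7.2 to each platelet pair**, assuming that white cells and neutrophils are acceptable.

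| 8 h count | 24 h count | Result on the text |
|---|---|---|
| above 75,000 | any | full dose, no repeat called for |
| 50,000-75,000 | 50,000-75,000 | reduced to 1 mg/kg |
| below 50,000 | below 50,000 | discontinued, if this counts as persisting |
| 50,000-75,000 | above 75,000 | no express rule; full dose by implication |
| below 50,000 | above 75,000 | no express rule; full dose by implication |
| below 50,000 | 50,000-75,000 | neither rule met |
| 50,000-75,000 | below 50,000 | reduction not met; persistence not yet shown |

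The first row stands for three pairs, so the table covers all nine. Two remain unassigned. The sixth row is the anomaly: 45,000 then 60,000 literally escapes the reduction that 60,000 then 60,000 receives. For this course footnote 2, which looks to the repeat, and 4.7.1, which needs both values, also point in different directions.

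**3. Neutrophils.** Take 1,000 at 8 h and 1,500 on the repeat. Under 4.7.1 the 8 h value lies between 800 and 1,200, and no second value is required, so the dose can be read as reduced. Under footnote 2 the repeat guides the dose and is above 1,200, so it can be read as full.

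**4. Timing.**

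- The repeat count is optional and may be drawn at any time up to 24 h, but the platelet reduction needs a 24 h value. If the repeat is omitted or drawn earlier, the rule cannot be evaluated as written.
- A count drawn at 24 h falls at 12 + 24 = 36 h to 20 + 24 = 44 h from the start of infusion 1. That is exactly at the 4.5.2 gap limit. The protocol gives no laboratory turnaround; if it is assumed to be 1 to 4 h, the result is known 1 to 4 h past the limit.
- Against the 60 h cap, 60 - 44 = 16 h to 60 - 36 = 24 h remain at the draw, and 12 to 20 h after a 4 h turnaround. The minimum for infusion 2 is 8 h, so the cap can still be met.
- The 4.7.2 clock runs to 24 h past the scheduled infusion time, which is itself 12 to 24 h after completion of infusion 1. It therefore ends 12 + 24 = 36 h to 24 + 24 = 48 h after completion, past both the 24 h gap limit and the last repeat count described.

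**5. Size.** The full regimen is 0.5 + 2.0 = 2.5 mg/kg and the reduced regimen 0.5 + 1.0 = 1.5 mg/kg. The difference is 1.0/2.5 = 40%.

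**The case against.** The strongest reply is that participants are not left unprotected. Section 4.1 makes dose 2 conditional on values above a threshold, and 45,000 is below every platelet cut-off in 4.7.1 and 4.7.2. The 4.7.2 clock is still running at 24 h, so a count that has just fallen below 50,000 may yet qualify as persisting. The best-interest clause allows the investigator to stop. This stands, and it is why the falling course is described only as not clearly assigned. It does not settle the rising course, and a threshold left undefined in 4.1 does not choose between full and reduced dose.

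Four stronger readings are tempting, but the text does not support them.

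- A reader might infer that falling or recovering counts in general have no rule. Counts above 75,000 at 8 h are covered, and recovery above 75,000 leaves the full dose standing by implication.
- A reader might infer that the 24 h count always misses the deadline. The draw falls at the limit, the limit is worded as *should*, the turnaround is not stated, and the 60 h cap can still be met.
- A reader might infer that footnote 2 makes the repeat count decisive. It says *inform*. It agrees with 4.7.1 when both counts are in the band, and the reading of the neutrophil limb that creates the conflict is one of two.
- A reader might infer that 80% of the ATG dose (2.0 of 2.5 mg/kg) turns on this ambiguity. Between reduced and full regimens the difference is 40%.

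Figure 7 may also settle some of the mixed cases. If it does, the text still has to match it.

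On frequency, entry excludes platelets below 100,000. Section 6.2.1 puts severe thrombocytopenia at up to 3%, at doses 4 to 5 times those proposed, and reports no concern about prolonged leukopenia or thrombocytopenia in the pilot study. That limits the reach of the point.

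**Conclusion.** The point holds in a limited form. On the text, platelets below 50,000 rising into 50,000-75,000 meet neither rule, although a count in the band throughout is reduced. Platelets falling from the band to below 50,000 are not clearly assigned. The neutrophil limb and footnote 2 allow two doses for a recovered count. The clocks in 4.5.2, 4.7.1 and 4.7.2 do not agree.

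Where the readings are reduced versus full dose, total exposure differs by 1.0 of 2.5 mg/kg (40%). The protocol gives no frequency for these courses at the planned dose; few of the 84 participants are likely to be affected, so the effect on the primary comparison should be small. The reason to act is that a stated safety rule gives an anomalous result and can be applied differently between sites.

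The conclusion assumes a literal reading of 4.7.1 and 4.7.2, a gap counted from completion of infusion 1 (supported by the 60 h reconstruction), and that Figure 7 does not already resolve the mixed cases.

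**What to change.** The sponsor should reconcile 4.1, 4.5.2, 4.7.1, 4.7.2, Appendix 1 footnote 2 and Figure 7. Every combination of first and repeat blood count should lead to one stated action, including courses that cross a band upward or downward and cases where no repeat is taken. The text should say which count or counts govern each limb, define the threshold in 4.1, and evaluate the rules on one clock consistent with the time allowed for dose 2. A single table that 4.7.1, 4.7.2 and Figure 7 all refer to would do this.

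Which action belongs to each combination, whether platelets and neutrophils follow the same logic, and when the repeat is drawn are for the clinical leads to decide.

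The cost is protocol wording and one table. Reconciling the text by itself adds no participants.
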